4.2 Study Endpoint

Primary endpoint:

- Phase completion of those who started a phase, the proportion who completed that phase, assessed for each phase of the Pivot program.
 - Phase completion is defined as completing the last in-app activity from that phase
 - Exception: completion of Secure is defined as being in Secure for 11 weeks, and having engaged with the program at least once within Secure (app open, daily check-in, responds to coach, logs cig), and providing smoking status (cigarettes per day and 7-day point prevalence) in the end-of-Secure questionnaire

Additional endpoints include:

Engagement:

- Weeks of active engagement
- Number of app opens
- Phase completion proportion of intention to treat (ITT) cohort that completes each phase
 - ITT cohort comprises participants who signed informed consent and completed onboarding in the Pivot app (i.e. downloaded the BSA and Pivot apps, completed device set-up, and completed the three guided breath tests, or GBTs)
- Program completion proportion of intention to treat (ITT) cohort who have been in Secure for 11 weeks and have engaged with the program at least once (open app, or complete a daily check-in, or respond to coach, or log a cigarette), and, provides smoking status (cigarettes per day and 7-day point prevalence) in end-of-Secure Survey

Smoking Behavior:

- Number of cigarettes smoked per day
- Quit attempts (participant did not smoke for at least 24 hours)
- Quit rates: 7-day, 30-day point prevalence

CONFIDENTIAL

- Assessed in the ITT cohort
- Assessed in the Per Protocol cohort (individuals who complete the end-of-phase survey in the phase during which the question is being asked or, complete the exit survey at the end of their engagement with the app, whichever occurs first)
- Sustained quit (continuous days quit)
 - Assessed in the ITT cohort
 - Assessed in the Per Protocol cohort
- Smoking reduction (in participants who do not quit smoking) proportion who achieved 50% cigarettes per day (CPD) reduction or more at study exit

Responses to questionnaires:

- Measurements assessing attitude toward smoking
 - o Readiness to quit
 - Goals related to smoking behavior
 - Confidence to quit
 - o Difficulty maintaining quit
- Net Promoter Score (NPS)
- NPS, for coaching
- Nicotine Dependence
- · Quality of Life

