Cigarette logging	Daily check-in asks if user smoked previous day, if so, then directs them to log cig.
Suggested breath CO sampling protocol	No explicit sensor use schedule, but sensor is incorporated as follows: • Encourage people who find the 3 times a day useful to keep doing that. • Allow users to set their own milestones, some can be sensor related. Pivot app also gives trophies for breath samples associated with abstinence to augment this. "Take a breath samples to celebrate your smoke-free success."
Coaching frequency	 3-4 coach-initiated interactions per week for the first 3 weeks For users who achieve 30day PP at 3 weeks or 7 weeks in Secure, coaching frequency drops to once weekly, until/unless user indicates lapse or relapse.
Study management	 For the first 3 weeks: If participant does not use the app at least once in 7 days (no cig logging, or CO sampling, or start/complete activity, or start/complete challenge, or complete daily check-in, or respond to coach outreach), study staff will email on day 9, text on day 10, call on day 12, and call on day 14 For the remaining 7 weeks: If participant does not use the app at least once in 14 days (no cig logging, or CO sampling, or start/complete activity, or start/complete challenge, or complete daily check-in, or respond to coach outreach), study staff will email on day 16, text on day 17, call on day 19, and call on day 21

The following table details the different questions being asked of participants at specific time points over the course of the study.

		1	1	1	T	I	I	1	1	T
	Baseline	Explore	Build	Mobilize	Quit (1wk)	Secure - 1wk (2wk post Quit)	Secure - 3wk (1mo post Quit)	Secure - 7wk (2mo post Quit)	Secure - End (3mo post Quit)	Follow -up (6mo)
Cigarettes per day	х	Х	Х	х	х	Х	Х	Х	х	х
Tobacco Forms Used	Х		Х		Х		х	Х	Х	Х
Readiness to Quit (1-10)	х	Х	Х	Х						
Success, if were to quit (1-10)	х	х	Х	Х						
Difficulty staying quit, (1-10)	Х	Х	Х	Х						
Quitting Goal	х	Х	Х	х						
Nicotine Dependence		Х		Х						
7day Point Prevalence					х	х	х	Х	Х	х
30day Point Prevalence							х	Х	Х	х
Date of Last Cig					Х	Х	Х	Х	х	Х
Longest Smoke- free Interval					Х	X	X	Х	Х	Х
Quit Attempts					Х	Х	Х	Х	х	Х
NPS		Х	Х	Х	Х				х	
Coach NPS		X	Х	Х	Х				Х	
Quality of Life	Х								Х	Х
Cessation Medications	х			Х	х	×	×	Х		Х

Participants will receive an email, text or phone call from study staff to inform them they have a questionnaire to complete (

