6.2 Data Analysis

Data from the run-in participants will be analyzed separately from the data from the general study participants. Both cohorts will be analyzed using the ITT and Per Protocol definitions, and endpoints described previously.

Changes in measurements from baseline, to the end of each phase, to exit will be assessed. Participants will serve as their own controls and comparisons will be made to no change. One sample t-test will be used for numerical data. Fisher's Exact or Chi square will be used for categorical data.

All deviations from the study protocol will be identified, recorded and analyzed.

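### Section 6.2 compares participants with themselves, but for categorical data it names only Fisher's exact or chi-square, which are not tests of within-person change (additional endpoints only)

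*Combined protocol and SAP*

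**What the plan says.** Section 6.2 (Data Analysis) states the comparison and then the tests.

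- Comparison: "Changes in measurements from baseline, to the end of each phase, to exit will be assessed". The null is also given: "Participants will serve as their own controls and comparisons will be made to no change".
- Numerical data: a one-sample t-test.
- Categorical data: Fisher's "Exact or Chi square will be used for categorical data".

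Nothing in the document says how the table for the categorical test is laid out, and no McNemar, Stuart-Maxwell or other paired categorical method is named.

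The categorical items asked repeatedly of the same people are in the questionnaire table of section 5.3:

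- "Quitting Goal", asked at baseline and in Explore, Build and Mobilize. Section 4.2 lists it among the additional endpoints as "Goals related to smoking behavior".
- "Tobacco Forms Used" and "Cessation Medications", asked at baseline and at several later points up to six months. Section 4.2 does not list them as endpoints.
- "7day Point Prevalence" and its 30-day counterpart, asked only after the quit date.

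**The concern.** When each participant is their own control, the information about change lies in the people whose answer differs between the two time points. A valid test must use that pairing. The t-test on change scores does; the two categorical tests named do not, and what goes wrong depends on the layout that section 6.2 leaves open.

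(a) **Time point by answer.** Each person is counted twice, as if in two separate samples. With positive within-person correlation, the usual case, the standard error is too large and a real shift can be missed.

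(b) **Baseline answer by follow-up answer.** The test asks whether the two answers are associated. They nearly always are, so a small p-value says nothing about change, and stable answers could be reported as a shift.

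Two analysts who both use the tests named in section 6.2 could therefore reach opposite conclusions from the same data.

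**Working it through.** **Plan's own figure.** Section 4.10 gives 260 enrolled and 100 or more completing at the last time point. It states no power or sample size for any categorical endpoint, so there is nothing to reproduce here.

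**Inputs.** From section 4.10: n = 100 and n = 260, taken as a plausible bracket for the number of pairs. Assumed, because the document does not give them: a binary item, two-sided 0.05, a 40% starting rate, and within-person correlation ρ from 0.1 to 0.7.

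**Model.** For rates p1 and p2, P(yes at both) = p1·p2 + ρ·√[p1(1−p1)p2(1−p2)]; the other three cells follow by subtraction. Each setting was simulated 40,000 times (4,000 for Fisher in layout (b)), with uncorrected chi-square.

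**Layout (a): the standard error.** Take 40% to 50%, n = 100, ρ = 0.5.

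- P(yes, yes) = 0.20 + 0.5 × √(0.24 × 0.25) = 0.3225.
- Switchers: 0.4 − 0.3225 = 0.0775 one way and 0.5 − 0.3225 = 0.1775 the other, 0.255 in total.
- Paired SE = √[(0.255 − 0.10²)/100] = 0.0495.
- SE if the samples are treated as independent = √[(0.24 + 0.25)/100] = 0.070.

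**Layout (a): simulated power.**

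| Setting | Test | ρ = 0.1 | 0.3 | 0.5 | 0.7 |
|---|---|---|---|---|---|
| 40% to 50%, n = 100 | chi-square | 30% | 27% | 24% | 18% |
| | Fisher | 25% | 22% | 18% | 12% |
| | exact McNemar | 27% | 33% | 43% | 67% |
| 40% to 50%, n = 260 | chi-square | 63% | 65% | 67% | 72% |
| | exact McNemar | 64% | 75% | 88% | 99% |
| 40% to 30%, n = 100 (e.g. point prevalence between two post-quit time points) | chi-square | 31% | 29% | 25% | 19% |
| | exact McNemar | 29% | 35% | 47% | 71% |

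**Layout (a): true size with no change.** At 40% both times, the variance of the difference is (1 − ρ) times what chi-square assumes, so its size is about 2·[1 − Φ(1.96/√(1 − ρ))] = 0.039, 0.019, 0.006, 0.0003 for the four correlations. Simulated at n = 100: 0.042, 0.019, 0.006, 0.0004.

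**Layout (b): no change, 40% both times.** The chi-square for association has noncentrality n·ρ².

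| ρ | n·ρ², n = 100 | chi-square rejects | Fisher rejects | n·ρ², n = 260 | chi-square rejects |
|---|---|---|---|---|---|
| 0.1 | 1 | 17% | 14% | 2.6 | 36% |
| 0.3 | 9 | 85% | 82% | 23.4 | over 99% |
| 0.5 | 25 | over 99% | over 99% | 65 | 100% |

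The percentages are simulated; the noncentral chi-square formula gives 17%, 85% and 99.9% at n = 100. The reverse failure also occurs: with a true change from 30% to 45% and ρ = 0, the layout (b) chi-square rejects in only 5.1% of samples at n = 100.

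**One data set, three answers.** Take 100 people, 40 answering yes at each time, 12 switching each way (cells 28, 12, 12, 48).

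- Layout (a): 40/60 against 40/60, chi-square 0, p = 1.0.
- Layout (b): 100 × (28×48 − 12×12)² / (40×60×40×60) = 25.0, p = 0.0000006 (Fisher p = 0.0000009).
- Exact McNemar: 12 against 12, p = 1.0.

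**The case against.** The strongest reply is that section 6.2 fixes the null as no change, so an analyst who tests association has left the plan, and the worst figures belong to that analyst. Chi-square might also mean McNemar's chi-square, that is, switchers tested against an equal split, which gives p = 1.0 in the example. Both points soften the charge. But the McNemar reading is nowhere stated, and Fisher's exact, named beside chi-square as the alternative, cannot be read that way. Another one-sample reading, testing follow-up answers against the observed baseline distribution as if it were fixed, does not help: with no change at n = 100 it rejects 15%, 10%, 5.5% and 1.2% at correlations 0.1, 0.3, 0.5 and 0.7.

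Several limits do stand.

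- Reach is about one listed endpoint, the quitting goal. Point prevalence has no baseline item, and section 6.2 does not explicitly plan comparisons between post-quit time points.
- The figure of 100 is for the last time point, while the quitting goal is last asked in Mobilize. Its number of pairs is not given; 100 and 260 only bracket it.
- The answer format of the quitting goal is not given. The binary calculation illustrates the problem rather than predicting results for that item.
- Under layout (a) with positive correlation the error is conservative. At a correlation near 0.1 the loss is negligible, and exact McNemar is slightly weaker than chi-square there (27% against 30%).

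**Conclusion.** The concern holds, as a minor one. The categorical tests named do not fit the within-person design set out in the same section. Under layout (a) the cost ranges from nothing at correlation 0.1 to a fall in power from 67% to 18% at 0.7 (n = 100, 40% to 50%). Under layout (b) the test does not address change and, with no change, rejects in 17% to over 99% of samples for correlations 0.1 to 0.5. These sizes rest on assumed rates, correlations and a binary item; the mismatch itself does not. It touches additional endpoints and questionnaire items only. Phase completion, cigarettes per day, the 1-10 ratings and the stated sample size do not depend on it.

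**What to change.** In section 6.2, for within-person categorical change, replace Fisher's exact or chi-square with McNemar's test for binary items (stating exact or asymptotic) and Stuart-Maxwell for items with more than two categories, or Wilcoxon signed-rank if the answers are ordered. Report the number of complete pairs for each comparison. Fisher's exact and chi-square can remain for comparisons between independent groups.

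The cost is one sentence and no new data. Only participants with both measurements contribute, as is already true of the planned t-tests on change. If exact McNemar is chosen, there is the slight loss of power at very low correlation noted above.

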4.1 Study Design

CONFIDENTIAL

,
This is a prospective open-label clinical trial conducted with IRB approval in up to 310 subjects who report daily smoking (up to 50 run-in subjects, and 260 general subjects). Potential
subjects will be recruited and prescreened as described in section 4.4
Potential participants will complete the Online Screening Form
Screening Form submission will be reviewed by study staff. Eligible participants and those of
uncertain eligibility (ex. potential participant's Online Screening Form was incomplete) will be
contacted by phone by study staff or the clinical recruiter to confirm eligibility, provide more
details about the study, and answer any questions the potential participant may have.
Eligible potential participants who remain interested in participation will be emailed the web
registration link. This link, along with the phone call that occurred previously, will be used to
verify the potential participant's identity. During the identity verification portion of the online
registration process, the potential participant enters contact information and verifies their identit
through a link sent to the email address they provide
Every online submission from a potential participant will be reviewed by study staff and any
discrepancies will be addressed through a phone call and/or possible videoconference with the
potential participant (for example, more than one online submission with the same name,
address, email address or phone number). Should a videoconference be pursued, such
communication will occur in a private office setting with only necessary study staff present and
the privacy of the potential participant protected (office door closed; screen not visible to anyone
other than necessary study staff; headphones used if possible, if not possible, volume at the
lowest level that allows for coherent dialogue).
After verification of eligibility and identity, potential participants will be asked to provide informed
consent. Potential participants will have the opportunity to ask questions of the study
investigator team during the informed consent process. Those who agree to participate will electronically sign the informed consent form
Study staff must review the eligibility and identity criteria, document the resolution of any
discrepancies from the identity verification process, answer any questions during the informed
consent process, and confirm informed consent is signed before approving a participant for
entry.

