4.3.1 Criteria for All Participants

All participants must meet all inclusion criteria:

- 18-65 years of age
- English speaking
- Smokes daily
- Smokes 5 or more cigarettes per day
- Owns and uses a smartphone (iPhone 5 and above, operating system iOS 9.0 and above, or, Android 4.4 and above, operating system Android 4.4 and above)
- Employed at least 20 hours per week
- Lives in the USA
- Understands and willing to sign the Informed Consent Form

While pregnant women are not specifically sought in this study, pregnancy is not an exclusion criterion, and pregnant women would be eligible should they meet the inclusion criteria and wish to participate. Pregnant women would be considered eligible for the following reasons: the risk profile of the device, the fact that recording smoking in the study is by self-report and the CONFIDENTIAL

modest participant stipend is not linked to smoking in any way, and potential participants reach out to the study team if they are interested in participating (i.e. recruitment is passive and wholly at the initiation of potential participants, who the study team have no visibility to unless contacted by the potential participant). While participants are deemed eligible to enter the study based on their self-report of smoking at least 5 cigarettes a day, they are not required or asked to smoke any particular amount (or at all) over the course study. Participants are asked to provide breath samples in the CO Breath Sensor device throughout the day, as they are able.

The general study (n=260) will employ non-proportional quota sampling as follows to ensure the study population mirrors the expected initial intended user population:

Age	18-29 year olds	30-60 year olds	61-65 year olds
	< 20 % of sample	Remainder	< 10 % of sample
Cigarettes Per Day (CPD)	5-10 CPD	11-30 CPD	> 30 CPD
	< 25 % of sample	Remainder	< 10 % of sample
Stages of Change*	Quit 30 days	Quit 6 months	Not interested
	≥ 20% of sample	≥ 20% of sample	≤ 20 % of sample
Sex	Male 40-60%	Female 40-60%	

^{*}Stages of Change question and answer choices: Are you seriously thinking of quitting smoking? A. Yes, within the next 30 days B. Yes, within the next 6 months C. No, not thinking of quitting

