4.10 Sample Size and Justification

Up to 50 participants will comprise the run-in group. The purpose of the run-in group is to provide baseline observations on the functioning of the BSA and Pivot app, and provide the opportunity to address unforeseen bugs or issues that arise prior to proceeding with the general study.

The target enrollment of 260 for the general study is estimated to yield 100 or more subjects completing the study at the last time point (3 months after the end of Secure). Based on power calculations, this will detect a 50% reduction in cigarettes, a mean change of 1 or greater in ratings assessing attitudes towards smoking, and will provide adequate confidence intervals to make historical comparisons.

5 Study Procedure and Schedule

5.1 Screening and Day 0

Study personnel will verify eligibility by reviewing the potential participant's responses to the Online Screening Form ; eligible participants (applies to both the run-in and general study participants) who meet non-proportional quota sampling needs (applies to general study participants) will then be called by study staff. During this call, any additional needed screening information is obtained, eligibility is confirmed, the study is described and the potential participant has the chance to ask questions. If the potential participant would like to proceed, the online registration form is emailed to the potential participant. Potential participants will be provided an access code at this time to allow access to the website.

Verification of identity and informed consent is performed during the screening phone call and during the online registration process. At this time, potential participants create a user login and password. An email is then generated and sent to the email address provided by the potential participant. To confirm identity, the potential participant must access their email and confirm through the provided link. The potential participant then reviews the electronic informed consent form on their own timeline and is provided study staff contact information should they have any questions. If the potential participant would like to proceed, they electronically sign the informed consent form

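### Read literally, section 6.2 tests quit rates against a 0% baseline fixed by eligibility, and the historical comparison invoked in 4.10 is not defined, so neither supports inference about the programme

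*Combined protocol and SAP*

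**What the plan says.** **Analysis (6.2).** The plan opens its inferential part with "Changes in measurements from baseline, to the end of each phase, to exit will be assessed", followed by "Participants will serve as their own controls and comparisons will be made to no change". Numerical data get a one-sample t-test, and "Fisher's Exact or Chi square will be used for categorical data". The section applies this to the ITT and Per Protocol definitions and to the endpoints already described. It gives no null or reference rate for quitting.

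**Endpoints (4.2).** "Quit rates: 7-day, 30-day point prevalence" is listed among the additional endpoints, for ITT and Per Protocol. The primary endpoint is phase completion: "of those who started a phase, the proportion who completed that phase, assessed for each phase of the Pivot program".

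**Eligibility (4.3.1).** Participants must smoke daily, and a further criterion reads "Smokes 5 or more cigarettes per day". The general-study quotas require at least 20% who are thinking of quitting within 30 days and at least 20% within 6 months, and allow at most 20% who are not thinking of quitting.

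**Questionnaire table (5.3).** 7-day point prevalence is first asked at the end of Quit, and 30-day point prevalence at week 3 of Secure. Neither is asked at baseline.

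**Sample size (4.10).** 260 enrolled are expected to yield 100 or more at the last time point. One of the reasons given for this size is that it "will provide adequate confidence intervals to make historical comparisons". No comparator, outcome, rate or interval width follows.

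**Design (4.1).** "This is a prospective open-label clinical trial conducted with IRB approval in up to 310 subjects who report daily smoking". No control arm is described.

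**The concern.** A change from baseline can be tested against no change when the baseline value is free to vary. Quit status at entry is not: the eligibility rule sets it to not abstinent for everyone. If 6.2 is followed as written for this categorical endpoint, the comparison is with 0%, and a very low quit rate is enough for significance.

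Zero is also not the rate to expect without the programme. The quotas deliberately bring in people who already intend to quit, so some quitting would occur anyway. A significant result against zero could then be read as evidence that the programme works, at a rate no better than unaided quitting in such a sample.

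The other reference that the protocol mentions, in 4.10, does not fill the gap. It has no content that could be applied to an observed quit rate.

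**Working it through.** **The plan's own figure.** Section 4.10 gives 260 enrolled and 100 or more completers, which is 100/260 = 38.5%. The power calculation behind it cannot be reproduced, because no SD, alpha, power, null rate or interval width is stated. It contains no quit-rate target.

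**Step 1: the implied null.** Daily smoking is required at entry, so 7-day and 30-day abstinence at baseline are 0 of n. This is an inference from 4.3.1; the protocol does not state it as a null.

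**Step 2: how few quitters reach significance.** Apply Fisher's exact test to 0/n against k/n. Because one cell is zero and the two groups have equal size, the two-sided p-value is 2 × C(n,k) / C(2n,k).

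| n | k | Rate | Two-sided p |
|---|---|---|---|
| 260 | 5 | 1.9% | 0.061 |
| 260 | 6 | 2.3% | 0.030 |
| 100 | 5 | 5.0% | 0.059 |
| 100 | 6 | 6.0% | 0.029 |

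This layout treats the same people before and after as two independent groups. That is one literal application of the named test, not a recommended one. A strict one-sample null of 0% is more extreme still: P(at least 1 quitter) = 0 under it, so a single quitter would reject.

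**Step 3: how often a programme with no effect would pass.** The documents give no unaided quit rate, so p is an assumption shown over a range. P(X ≥ 6) with X ~ Binomial(n, p):

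| Assumed unaided rate p | n = 260 | n = 100 completers |
|---|---|---|
| 3% | 79% | 8% |
| 4% | 95% | 21% |
| 5% | 99% | 38% |
| 10% | over 99.9% | 94% |

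In the full cohort the test passes with high probability across this range. Among 100 completers it does so only towards the upper end.

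**Step 4: what a real benchmark would require.** Take p0 as an assumed benchmark and find the smallest count r with P(X ≥ r | n = 260, p0) ≤ 0.025:

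| Assumed benchmark p0 | Quitters needed of 260 | Rate |
|---|---|---|
| 2% | 11 | 4.2% |
| 5% | 21 | 8.1% |
| 10% | 37 | 14.2% |
| 15% | 52 | 20.0% |

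The test in Step 2 needs 6. The choice of reference therefore decides the conclusion, and 4.10 leaves it open.

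**Step 5: estimation and denominator.** Exact (Clopper-Pearson) 95% intervals at n = 260 are 6.6% to 14.3% for 26 quitters (10%) and 15.3% to 25.4% for 52 (20%). These are usable as description. The denominator must be fixed as well: 30 quitters is 30% of 100 completers (21.2% to 40.0%) but 11.5% of 260 (7.9% to 16.1%).

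**The case against.** The best reply is that 6.2 never says quit rates are tested against 0%. The sentence about no change follows one about changes from baseline. Point prevalence has no baseline measurement, so quit rates may simply be meant as reported proportions, and the categorical tests may be intended for items such as quitting goal. The study is open-label and single-arm, states no efficacy hypothesis, and lists quit rate as an additional endpoint. Section 4.10 already speaks of confidence intervals and does not say that the historical comparison concerns quitting.

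Much of this stands, and it rules out several stronger readings that a reader might infer:

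- *That every outcome is compared with no change.* Phase completion, app opens and Net Promoter Score have no baseline, so the phrase is undefined for them. For cigarettes per day and attitude ratings it is a definable null.
- *That the quit rate has no value.* It can be estimated with an interval; only attribution to the programme is affected.
- *That a benchmark would be picked after the results are known.* The documents do not say when one would be chosen. The empty reference list proves nothing, because its content may have been removed from this text.
- *That an ineffective programme would always pass.* Step 3 gives 79% at 3% in 260 people, and far less among 100 completers.

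The reply does not remove the literal reading. Section 6.2 covers the listed endpoints, quit status is categorical, and no other analysis is given for it. Nor does it supply the comparator missing from 4.10.

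**Conclusion.** The point holds, and the plan should be changed. Taken as written, 6.2 permits a significance test of quitting that 6 of 260 participants (2.3%, p = 0.030) would pass. A programme with no effect would pass it with probability about 79% to 99% at assumed unaided rates of 3% to 5%. Section 4.10 rests part of its sample-size argument on a comparison that no section defines.

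This assumes that the categorical tests in 6.2 extend to quit rates, that the baseline is the 0% implied by eligibility, and that unaided quitting lies in the range shown. The first two are inferences from the text and the third is an assumption. The weakness concerns inference about the programme from an additional endpoint. It does not touch the primary endpoint or the estimation of quit rates.

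**What to change.** **Section 6.2.** Limit the comparison with no change to outcomes measured at baseline whose value can vary: cigarettes per day, attitude ratings and quality of life. For 7-day and 30-day quit rates, make no test against baseline. Report the ITT proportion with an exact 95% confidence interval, labelled descriptive.

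**Section 4.10.** Choose one of two:

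- Delete the reference to historical comparisons and state that quit rates are not attributed to the programme.
- If the comparison is kept, fix one benchmark rate before general-study outcomes are reviewed, with matching abstinence definition, time point and ITT denominator.

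**Cost.** The first option is a few sentences and needs no new data. The sponsor gives up a p-value for quitting and makes a more modest claim. The benchmark option costs more, because it needs an external rate that the documents do not supply.
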